## 1. Version History

Version	Summary of Changes	Author(s)/Title
1.0	Not Applicable, New Document	[name], Prin. Statistician

## 2. List of Abbreviations and Definitions of Terms

Abbreviation	Definition
AD	Addendum
ADaM	Analysis Dataset Model
ADE	Adverse Device Effect
AE	Adverse Event
AP	Analysis Plan
CER	Clinical Evaluation Report
CI	Confidence Interval
CIP	Clinical Investigation Plan
CRF	Case Report Form
DD	Device Deficiency
eCRF	Electronic Case Report Form
FDA	Food and Drug Administration
IC	Informed Consent
ICF	Informed Consent Form
IRB	Institutional Review Board
LAR	Legally Authorized Representative
MedDRA	Medical Dictionary for Regulatory Affairs
PI	Principal Investigator
PAS	Post-Approval Study
PSR	Product Surveillance Registry
SADE	Serious Adverse Device Effect
SD	Standard Deviation
SAE	Serious Adverse Event
SAP	Statistical Analysis Plan
SI	Surgical Innovations
SR	Surgical Robotics
TLG	Tables, Listings and Graphs

## 3. Introduction

In 2011, Medtronic launched the global Product Surveillance Registry (PSR). It was built on more than 25 years of post-market clinical surveillance experience and designed to provide continuing evaluation and periodic reporting of safety and effectiveness of market-released products for their intended use.

Data collected in the PSR supports post-market surveillance activities and post-approval studies initiated by Medtronic, regulated by local governments, or conducted to fulfill government and/or regulatory

authority requests. The PSR also obtains clinical evidence to guide the development and improvement of medical devices, therapies, device guidelines, patient services/solutions and provide clinical data to support health economics and clinical outcomes research.

The PSR supports multiple Medtronic Surgical Innovations (SI) and Surgical Robotics (SR) products used in a wide range of surgical and medical procedures including minimally invasive procedures, robotic procedures, endoscopic procedures, and percutaneous procedures.

This Statistical Analysis Plan (SAP) is designed to document, before data is analyzed, the planned statistical analyses, and to support regulatory reports and *ad hoc* data requests. Reports generated using the PSR data may not contain all the objectives described below; however, if a report contains an objective outlined within this document, the analysis of that objective will be performed as described in this SAP. If additional analyses are required but not covered in this SAP, a study specific SAP addendum may be developed. A thorough explanation and rationale for any analyses conducted differently than outlined in the PSR Surgical Platform Base Clinical Investigation Plan (CIP) or SAP will be provided in conjunction with the analyses/output.

The following document was used to create this SAP: Product Surveillance Registry Platform Base Clinical Investigation Plan, Version 9, 19 May 2020 and its Surgical Appendix, Version 2, 07 Dec 2020.

## 4. Study Objectives

The objective of PSR Surgical Platform is to serve as an ongoing source of product performance, patient safety and clinical outcomes information associated with the use of market released Medtronic products for surgical innovations and surgical robotics.

### 4.1 Primary Objective

The primary objective is to evaluate the safety and performance of Medtronic market released products for surgical innovations and surgical robotics. The objectives include, but are not limit to the following:

- To estimate the surgical or medical procedure related and/or the product related event rate
- To characterize the surgical or medical procedure related events and/or the product related events

Depending on the products, the primary endpoint may be assessed at different time point, e.g. after procedure, 30-day post procedure, or 5 years post procedure. For details, please refer to the study protocol.

### 4.2 Secondary Objective

The secondary objectives are intended to gain additional information about safety and performance of the products for surgical innovations and surgical robotics. There are no established performance goals related to the secondary objectives.

For products following the short-term schedule, the following variables/outcomes will be evaluated to gain additional information, but are not limited to:

- Procedure details including intra- and post-operative assessments
- Incidence of specific events during or post procedure

- Mortality
- Length of hospital stay
- Readmission rate
- Reintervention rate
- Product related events
- Device deficiencies (DD)

For products following the long-term schedule, in addition to the variables/outcomes listed above, the overall survival, study-specific survivals may be carried out for safety and performance evaluation.

This SAP intends to cover the objectives specified above. For any objectives described in the study protocol or addendum, but not listed here, they will be included in study-specific SAP addendum. Please refer to study-specific SAP for the details regarding primary and secondary objectives if they are not included in this SAP.

## 5. Investigation Plan

### 5.1 Study Design

The PSR is designed to conduct active prospective post-market surveillance. Its extensible design allows products to be easily added following market release. Only subjects treated with an eligible product can be enrolled. Data collection is intended to align with routine clinical care practice.

The PSR Platform Base CIP format has a modular design which provides a framework for the collection of surveillance data to support Medtronic's product portfolio. The PSR Platform Base CIP for a given Condition/Therapy is comprised of the following:

- PSR Core: defines elements applicable to all PSR subjects, products, conditions, or therapies
- PSR Condition/Therapy Appendix: expands on the content of the PSR Core to further define specific procedure and data collection requirements for a given Condition/Therapy and is intended to align with routine care practices

PSR Surgical Platform base CIP includes PSR Platform Base CIP and its Surgical Appendix. Specific analysis requirements for each study are documented, as applicable, and are integrated with the CIP in one of two ways, either via an associated Analysis Plan (AP) or Addendum (AD). This SAP intends to cover most common objectives described in the above documents and provides statistical analysis details. In case any of the objectives or specific analysis is not covered, they will be included in SAP addendum.

Together, this SAP and its SAP addendum comprise the study-specific SAP.

### 5.2 Duration

Overall, the PSR has no anticipated end date. However, for each individual study, the duration is determined by multiple factors, such as objectives and enrollment. It varies from study to study.

## 5.3 Study Population

Subjects treated with an eligible Medtronic market released surgical product(s) and enrolled within the enrollment window are eligible to participate in the PSR with additional inclusion/exclusion criteria listed below. Not all Medtronic market released surgical products are required to be included into the PSR Surgical platform. Product eligibility is based on the determination that there is an interest or requirement for obtaining additional information to further characterize product performance following market release.

## 5.4 Eligibility

### 5.4.1 Inclusion Criteria

- Subject or legally authorized representative (LAR) provides authorization and/or consent per institution and geographical requirements
- Subject has, or is intended to receive or be treated with, an eligible Medtronic surgical product
- Subject is consented within the enrollment window of the therapy received, as applicable

### 5.4.2 Exclusion Criteria

- Subject who is, or is expected to be, inaccessible for follow-up
- Subject is excluded by local law
- Subject is currently enrolled in, or plans to enroll in, any concurrent drug/device study that may confound the PSR results (i.e. no required intervention that could affect interpretation of all-around product safety and/or effectiveness)

Additional criteria may be required, refer to Condition/Therapy Appendix for further guidance.

## 6. Determination of Sample Size

The sample size calculation is based on the primary objective and serves to ensure sufficient precision for characterization of product performance. The exact definition of sufficient precision will vary based on the intended use of the data and product type. The general concept is that sample sizes should be large enough to generate meaningful estimates for population parameters of interest.

### 6.1 Sample size determination for event rate

To estimate sample size based on event rate and its pre-defined 95% confidence interval (CI), binomial distribution will be used. Assuming the event rate is  $\hat{p}$ , the sample size,  $N$  is estimated using the following expression (Rosner).

$$N = \frac{1.96^2 \times \hat{p}[1 - \hat{p}]}{(halfwidth)^2}$$

where *halfwidth* is half of the 95% CI width. The table below shows the sample size estimates when the event rate is ranged from 5% to 20% and *halfwidth* is from 5% to 10%.

Event Rate \ Halfwidth	5%	7.5%	10%
5%	73	-	-
10%	139	62	-
15%	196	88	49
20%	246	110	62

## 6.2 Sample size for characterization of events of interest

To characterize the surgical or medical procedure related and/or the product related events, the sample size should be large enough to ensure at least one event observed with high probability, e.g. >90%, if the event rate has been reported. Otherwise, a sample size of 20-50 is recommended to provide a reasonable estimate.

The actual enrollment size for different products may vary due to regulatory requirements, sale volumes, attrition rates and manufacturing changes, etc. Enrollment will continue until a sufficient sample size is achieved to assess product performance. This sample based on Registry enrollments is representative of the worldwide population, and therefore the estimates shown should be representative of the worldwide performance of these models.

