4.2. Purpose

The purpose of the PSR is to provide continuing evaluation and periodic reporting of safety and effectiveness of market-released products for their intended use. PSR data will support post-market surveillance activities and post-approval studies that are initiated by Medtronic, regulated by local governments, or are conducted to fulfill government and/or regulatory authority requests. The PSR will also obtain clinical evidence to guide the development and improvement of medical devices, therapies, device guidelines, patient services/solutions and provide clinical data to support health economics and

clinical outcomes research. Conducting product surveillance in populations over time provides an effective means of assessing product performance, patient safety and clinical outcomes. Product surveillance is the systematic collection, analysis, and interpretation of performance data, as well as its dissemination and application.

The PSR is designed to provide a repository of data for conducting signal detection activities for identification of emerging patient safety or performance issues. It is designed to obtain real-world performance and safety information from a global network of hospitals, clinics, and clinicians intended to represent the range of clinical environments in which Medtronic products are used. It provides a mechanism for gaining an increased understanding of the relationship between a product's performance and clinical outcomes, as well as improving patient safety by identifying potential performance trends.

The PSR data are intended to benefit and support interests of patients, hospitals, clinicians, regulatory bodies, payers, and industry by streamlining the clinical surveillance process and facilitating leading edge performance assessment via the least burdensome approach.

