4.3. Eligible Products

Eligible products include market-released products. Approved indications of use for each market-released product are defined in the Instructions for Use (IFU) and/or product labelling. Not all Medtronic market-released products are eligible for enrollment. Product eligibility is based on the determination that there is an interest or requirement for obtaining additional information to further characterize product performance following market release. Medtronic may limit enrollment using an Enrollment Guide typically when the number enrolled is adequate to effectively assess product performance or product availability is restricted.

5. Objectives

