6.3. Steps Taken to Minimize Bias

Sites must meet pre-defined criteria to be selected to participate in the registry. The following methods may be incorporated to further minimize potential bias:

- Sites will consider enrollment of all eligible patients
- Enrollment may be limited at a site level by product and/or by therapy
- Events may be adjudicated by an independent review committee, as determined by therapy or regulatory requirements
- Diverse geographical site representation
- Sites represent various types of practice settings including university, community, public and private
- Data may be assessed by an independent reviewer (e.g., Core lab) as determined by therapy
- Procedures and data collection requirements are standardized

In addition, confounding variables and factors will be taken into consideration during data analysis, as applicable. Confounding variables and factors may include, but are not limited to:

- Medical history (e.g., comorbidities, surgical history)
- Patient-related factors (e.g., age, sex)
- Concomitant therapies

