8.4. Exclusion Criteria

- Patient who is, or is expected to be, inaccessible for follow-up
- Patient is excluded by local law
- Patient is currently enrolled in, or plans to enroll in, any concurrent drug/device study that may confound the PSR results (i.e. no required intervention that could affect interpretation of all-around product safety and/or effectiveness)

Additional criteria may be required, refer to Condition/Therapy Appendix for further guidance.

9. Site Selection and Readiness

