9.1. Site Selection

Sites participating in the PSR are located globally. At a minimum, the following criteria will be met before sites are selected for participation:

- Site clinicians are or will be users of Medtronic products
- Site has strong interest in active post-market surveillance

- Site has adequate resources, facilities, equipment and support staff
- Site can comply with registry requirements, local laws or regulations, and Medtronic requirements
- Sites are responsible for ensuring practicing clinicians are appropriately licensed/qualified
- Sites are responsible to ensure practicing clinicians are not debarred, disqualified, or working under sanctions in applicable regions
- PI qualifications confirmed

The role of the principal investigator (PI) is to implement and manage the day-to-day conduct of the registry as well as ensure data integrity and the rights, safety and well-being of the patients involved in the registry. The PI shall be qualified by education, training and experience to assume responsibility for the proper conduct of the clinical registry in accordance with the CIP and applicable local regulations.

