Version history is maintained within a separate document.

Condition/Therapy Appendix: Surgical

A. Surgical and Medical Procedure Background

The Product Surveillance Registry (PSR) supports a wide range of surgical and medical procedures completed using one or more Medtronic products in open, minimally invasive, robotic, endoscopic, and percutaneous procedures.

Often classified as the 'traditional type' of surgery, open surgery occurs when incisions are made in a patient through which surgeons insert various instruments to conduct the surgery.

Minimally invasive surgery (MIS) is a technique where operations are performed through small incisions in the body whereby surgical instrumentation are inserted allowing the procedure to be performed with minimal tissue interruption (e.g. laparoscopic surgery).

Robot-assisted laparoscopic surgery utilizes a Robotic Assisted Surgical Device (RASD) to provide three-dimensional visualization and articulation of the robotic instrument wrists.

Additionally, endoscopic and percutaneous surgical procedures offer additional options to perform MIS. Endoscopic surgeries involve the insertion of a long, thin tube, typically with the use of a camera and light, directly into the body to perform a surgical procedure.

Percutaneous surgery is characterized by being done through one or more small puncture sites or minor incisions through the skin, often without direct visualization of the underlying anatomy.

Details on each of the market approved study devices (including e.g. device description, contraindications and potential complications) are included in the current applicable version of the Instructions for Use document.

B. Data Collection

Steps to minimize bias in the PSR Surgical patient population align with Section 6.3 (Steps Taken to Minimize Bias). These steps are followed to ensure enrollments are an appropriate representation of the patient population. Product specific known or foreseeable factors available in product labeling/IFU may be taken into consideration. Medtronic may limit enrollment using an Enrollment Guide to account for specific cohorts of product use and ensure adequate enrollments to effectively assess study objectives.

B.1 Enrollment

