#### 7.1.3 Analysis Sets

Subjects included in any analysis sets must consent to the PSR, unless a full waiver of consent has been approved by the site's IRB or EC, and meet all the inclusion/exclusion criteria. They must have been treated with at least one Medtronic market released surgical product. Additional inclusion/exclusion criteria include, but are not limited to specific components or models, time frame, data cutoff date and geography. For details, please refer to Analysis Plan (AP) or Addendum (AD).

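### SAP 6.2 states as fact that the registry sample represents the worldwide population, which the design neither ensures nor checks

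*SAP*

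**What the plan says.** The sentence closes SAP 6.2, after the rules for cohort size: "This sample based on Registry enrollments is representative of the worldwide population, and therefore the estimates shown should be representative of the worldwide performance". The first half is a flat assertion. The second half is softer, but it is drawn from the first by inference.

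Other parts of the two documents bear on it:

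- **Aim.** Protocol 4.2 describes a site network "intended to represent the range of clinical environments in which Medtronic products are used".
- **Bias steps.** Protocol 6.3, repeated in SAP 7.3, lists measures such as geographic spread and mixed practice settings, introduced by "The following methods may be incorporated to further minimize potential bias". Section B of the Surgical Appendix refers back to that list and adds: "These steps are followed to ensure enrollments are an appropriate representation of the patient population".
- **Site choice.** Protocol 9.1 sets minimum criteria for sites, one of which is "Site has strong interest in active post-market surveillance".
- **Patient choice.** Protocol 8.4 excludes a "Patient who is, or is expected to be, inaccessible for follow-up". Consent is needed unless it is waived or not required locally.
- **Analysis sets.** SAP 7.1.3: "Additional inclusion/exclusion criteria include, but are not limited to specific components or models, time frame, data cutoff date and geography".
- **Site share and pooling.** SAP 7.3 sets no ceiling on the percentage a site may contribute, keeps a sponsor right to limit or close a site, and pools all sites for the primary analysis. Protocol 14 offers 15% of projected enrolment as a guideline that may be used.
- **Uncertainty.** SAP 7.9.1.3 plans a two-sided 95% binomial interval for the event rate.

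**The concern.** Representativeness of a target population has to come from somewhere: from how units were sampled, from weighting or standardising to the target, or from a comparison showing that the sample resembles it. The SAP plans none of these and asserts the result anyway, in a platform document meant to serve many products and cohorts.

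SAP section 3 says the plan supports regulatory reports and ad hoc data requests. A report written under it could cite 6.2 as pre-specified grounds for reading its event rate as worldwide product performance. The only planned measure of uncertainty for that rate is an interval that assumes the sample is right and allows only for chance. Nothing requires a study-specific addendum to withdraw, qualify or test the sentence.

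**Working it through.** **1. The SAP's own figures.** The sentence carries no number. The nearest figures are the sample sizes in SAP 6.1, from N = 1.96² × p(1 − p) / halfwidth². For p = 10% and a half-width of 5 points: 3.8416 × 0.09 / 0.0025 = 138.30, rounded up to 139. All nine entries reproduce in this way (73; 139, 62; 196, 88, 49; 246, 110, 62). They concern chance error and say nothing about who is sampled.

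**2. What the claim needs, against what the documents provide.**

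| Needed | Provided |
|---|---|
| Sites drawn from worldwide users | Sites chosen on criteria that include interest in surveillance and resources (Protocol 9.1) |
| Patients drawn from all treated patients | Sites asked to try to approach every eligible patient (Surgical Appendix B.1), after excluding those expected to be hard to follow (Protocol 8.4) |
| Mandatory geographic and practice spread | Listed among steps that may be used (Protocol 6.3, SAP 7.3) |
| Worldwide analysis set | May be restricted by geography, model or time frame (SAP 7.1.3) |
| Bounded influence of one site | No ceiling in SAP 7.3; discretionary 15% guideline in Protocol 14 |
| Weighting to, or comparison with, the target | None; sites pooled (SAP 7.3) |

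If the 15% guideline were always applied, 1/0.15 = 6.7, so seven sites could still fill a cohort. Where no event rate has been reported, SAP 6.2 recommends 20 to 50 subjects and sets no minimum number of sites.

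**3. Size, on assumed values.** The documents give no event rates by type of site and no worldwide mix, so any size is illustrative. Assume two strata that each make up half of worldwide use, with the lower-rate stratum over-represented in the registry. The bias is b = worldwide rate − expected sample rate. With se = √(p_s(1 − p_s)/N), where p_s is the expected sample rate, coverage of the worldwide rate is Φ(b/se + 1.96) − Φ(b/se − 1.96).

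Worked case: rates 8% and 14%, sample mix 80:20. Then p_s = 0.8 × 8% + 0.2 × 14% = 9.2%, the worldwide rate is 11%, and b = 1.8 points. At N = 139, se = √(0.092 × 0.908/139) = 2.45 points and coverage is 88.6%.

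| Assumed rates | Sample mix | b (points) | Coverage, N = 139 | Coverage, N = 1390 |
|---|---|---|---|---|
| 8%, 14% | 60:40 | 0.6 | 94.4% | 88.7% |
| 8%, 14% | 70:30 | 1.2 | 92.4% | 67.5% |
| 8%, 14% | 80:20 | 1.8 | 88.6% | 35.9% |
| 5%, 15% | 60:40 | 1.0 | 93.0% | 74.4% |
| 5%, 15% | 70:30 | 2.0 | 86.0% | 21.5% |
| 5%, 15% | 80:20 | 3.0 | 71.7% | 0.8% |

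N = 139 is a SAP entry. N = 1390 is ten times that and is not in the documents; it shows that a larger cohort narrows the interval around the same biased value.

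**The case against.** The documents do more about representation than state a hope. The Surgical Appendix says its bias steps are followed so that enrolment suitably reflects the patient population, and B.1 asks sites to try to approach every eligible patient. Protocol 6.3 says confounders will be considered in analysis as applicable, and SAP 7.3 allows by-site summaries and exploratory work on centre heterogeneity. There is no hypothesis, and no endpoint, estimator or interval depends on the disputed sentence. All of this stands, and it limits the point to wording and inference. It does not rescue the sentence: the Appendix does not say worldwide, and it relies on a list that Protocol 6.3 makes optional.

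Three stronger readings are tempting and not supported:

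- **That the sample is unrepresentative.** A reader might infer this from the purposive choice of sites. The documents show only that representativeness is neither ensured nor checked.
- **That enrolment limits are themselves evidence of selection.** Protocol 4.3 says "Medtronic may limit enrollment using an Enrollment Guide", but typically once numbers are adequate or supply is restricted. Protocol 14 and SAP 7.3 present closing enrolment as a way to reduce bias.
- **That the reported interval would miss the worldwide rate.** Suppose participating-type sites have a 10% rate and 20% of use, and others 15%. The worldwide rate is then 0.2 × 10% + 0.8 × 15% = 14%. An interval centred on 10% excludes 14% only if 1.96 × √(0.09/N) < 0.04, that is N above about 216. At the SAP's own sizes for a 10% rate, 139 and 62, the half-widths are 5.0 and 7.5 points and the interval includes 14%, although the estimate is still centred 4 points low.

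Nor does the SAP say that a one-region analysis set may be reported as worldwide. It fails to exclude that reading.

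**Conclusion.** The assertion in SAP 6.2 is unsupported as written and should be changed. The design does not establish worldwide representativeness and plans no check of it, and the protocol and Surgical Appendix claim less than the SAP does. No sample size or analysis is wrong, and none changes with the correction. What changes is what a report may conclude.

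The size of any selection bias cannot be derived from the documents. The illustrations rest on assumed stratum rates, mixes and direction; the bias could run the other way or be negligible. They establish only the mechanism: the binomial interval does not reflect selection, and a larger sample does not remove it.

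**What to change.** Replace the sentence in SAP 6.2 with wording such as:

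> The registry aims to cover the kinds of clinical setting where the products are used. Estimates apply to the enrolled subjects at participating sites. Generalisation to worldwide use is not assumed, in particular for analysis sets restricted by geography or drawn from few sites.

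This keeps the aim stated in Protocol 4.2 and drops the inference that the design cannot carry.

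Have each report tabulate its analysis set by geography, practice setting and each site's share of subjects. SAP 7.3 already names the first two as site characteristics, and no new patient data appear to be needed. While editing 7.3, align its statement on site share with the 15% guideline in Protocol 14.

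The cost is the SAP wording, one descriptive table per report, and a less favourable claim.
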